### **6.5.2 Prior and concomitant therapy**

Descriptive analysis will be conducted on the method(s) of contraception used by each subject and the duration of use in the period immediately prior to participation in this study (prior to undergoing permanent sterilization). Summary analysis will be performed on the method of alternative contraception used during the period in which they are unable to rely on Essure or laparoscopic tubal sterilization. All concomitant medications used during the study and prior medications used up to 2 years prior to study participation will be summarized.

## **6.6 Confounder or bias adjusted analyses**

Due to the observational character of this study, the results are prone to bias and confounding. In the study protocol approaches related to study design are given that are intended to reduce bias during study conduct. This section describes how confounding will be addressed in the statistical analysis.

Confounding is a form of systematic bias in which the observed effect measure results from a combination of effect from treatment and effect from correlates of treatment which are independent risk factors for the AE and correlates of exposure. As a consequence, the observed effect measure differs in a systematic way from the true effect measure of the therapy. Therefore, methods to control for confounding will be employed in the analyses. By definition, confounding by indication goes hand in hand with unbalanced covariates, caused by the non-randomized treatment allocation (allocation bias).

To control for measured confounding at baseline in the analyses, the propensity score method as in Rubin (2008) [4] will be used to balance the analysis population with respect to baseline covariates by deriving a PS confounder-adjusted population. Based on all treated subjects (full analysis set, see Section 5.1) this population will be derived as described in Section 6.5.1. The analysis of the PS confounder-adjusted population is described in Section 6.5.2.

### 6.6.1 Development of propensity score

In order to assure that the PS is developed without knowing any outcome variables, the iterative model build process will be conducted by an outcome-blinded independent party which has only access to the treatment variable and the baseline variables listed in [Table 2](#).

The outcome variables will be removed from the data set during PS development; those constructing the score will not have access to any outcome information. Any variable measured after the treatment decision will be considered an outcome, as it could have been affected by the treatment.

The initial sterilization treatment will be considered the “treatment” for the purpose of the PS analyses.

All baseline variables will be considered for inclusion into the model; however the variables in [Table 5](#) have shown previous evidence to likely be included in the model. The decision to keep them or to remove them from the model or to alter the level of scale will be decided during the build of the score using analysis diagnostics as described below. A detailed report on the procedures applied for selection of variables and for considerations for analyses will be provided by the independent party.

**Table 5 - Baseline variables suspected to be included in PS modela**

Variables
Age
Race
BMI
US Geographical Region
Insurance type (Government-subsidized program, Commercial/Private , Other)
Hormonal Contraception Use At Baseline
Pre-existing abnormal uterine bleeding
Disorders associated with hysterectomy (fibroids, ovarian pathology, endometriosis, prolapse, hyperplasia)
GI disorders (e.g., IBS)
Pre-existing Autoimmune Disease
Pre-existing Diabetes
Pre-existing Hypertension

a Based on internal data on file

The approach to take would be to first construct the PS model and estimate the PS in both groups, assess the overlap, and determine if a PS confounder-adjusted analysis can proceed based on the overlap.

Logistic regression will be used to model the relationship between the background variables and the treatment, and a PS will be estimated for each subject by a fitted value from the logistic regression.

In an effort to improve model fit several steps can be investigated, including dichotomization or grouping of baseline variables intended for inclusion in the model.

In a first step, all above listed potential confounders are to be included in the stepwise model build procedure.

In a second step, all other baseline data plus the list of potential confounders used for model build in the first step will be included in a stepwise logistic regression procedure.

The two models will be compared. If the contribution of the additional data is low, the PS built on the first model will be considered for analysis. The independent party will assess this and propose the final model. This proposal will be discussed with the FDA.

Use of 1-to-1 nearest neighbor matching with a caliper of 0.2 SD of the logit Propensity Score will be the preferred procedure in order to ensure comparability. (Austin 2011 [5], Rosenbaum and Rubin 1985 [6])

Numerical and graphical balance diagnostics will be produced to assess the resulting similarity between treatment groups. Balance will be examined for individual background variables, for logs and squares of continuous background variables, for two-way interactions between background variables, and for other pre-specified combinations of variables. The intent is to properly specify the PS model, but also considering the potential to overfit—as this would reduce PS overlap. Inclusion of factors that are highly predictive of treatment choice but that adversely impact on ability to balance important known confounders should be carefully selected. If such factors exist, they must be reported, as they are also indicative of potential limitations to the interpretation of study results. While the intention to generate an overlap of PS density functions in absence of such predictors of treatment choice would still enable a technical conduct of analyses, it would on the other hand require that these predictors are not outcome associated. Such consideration must be made when omitting strong predictors for treatment choice from the PS Model. A percentage of desired overlap between density functions is not a priori determined. Generally, a loss of patients for the adjusted safety analysis set of less than 15% would be covered by the sample size considerations.

During the iterative process, some subjects may be removed from the analysis population in order to improve the balance between covariates. These subjects will be flagged in the subject listings on AEs.

In case missing data are obtained in the set of confounders, despite the quality assurance measures, it must be decided whether missing data will be utilized as its own category in the PS design or whether subjects with missing data in any variable should be disregarded or imputed in the PS design. This would depend on the magnitude of cases with missing data. The independent party will assess this during PS build and recommend on the procedures for addressing missing data.

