- Characteristics of subjects undergoing Essure Confirmation Test compared to subjects who do not comply with the requirement for Essure confirmation testing.

Statistical analyses will be explorative and descriptive in nature and no confirmatory hypothesis tests are intended to be performed; p-values will be interpreted as a metric for uncertainty. Therefore, no adjustment for multiplicity will be necessary.

All endpoints and variables will be analyzed by descriptive statistical methods. The number of data available and missing data, mean, standard deviation, minimum, lower and upper quartiles, median, and maximum will be calculated for continuous data. Frequency tables will be generated for categorical data. They will include the number of missing values as additional categories. Relative frequencies will be shown as percentages which will be calculated as a proportion including the category of missing values. Incidence rates and proportions will be used to summarize main endpoints and other variables. For time-to-event endpoints, hazard ratios derived from a Cox regression model, and Kaplan-Meier estimates will be provided.

If not specified otherwise, the analyses are presented in a way that events will be assigned to the treatment which was given initially at the index event.

The main analyses will be performed on a PS confounder-adjusted population of the Full Analysis Set in order to adjust for measured confounding as well as on the Full Analysis Set population. After all subjects have been enrolled, an outcome-blinded independent party, which only has access to the treatment variable and baseline variables, will perform the PS matching. All baseline variables will be considered for inclusion into the model; however, the following variables have shown previous evidence to likely be included in the model: age, race, BMI, US geographical region, insurance, hormonal contraception use at baseline, pre-existing pain disorders (pelvic pain, low back pain, chronic headache, fibromyalgia), disorders associated with hysterectomy (fibroids, ovarian pathology, endometriosis, prolapse, hyperplasia), gastrointestinal disorders (e.g., irritable bowel syndrome), pre-existing autoimmune disease, pre-existing diabetes, and pre-existing hypertension.

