### **3 Study design**

This study is a multicenter, open-label, non-randomized, continuous enrollment, prospective, observational postmarket surveillance study.

Study subjects will be women who are seeking permanent contraception and who have elected to undergo either hysteroscopic sterilization (Essure System ESS305) or laparoscopic tubal sterilization. Candidates who meet the inclusion and exclusion criteria, are willing to participate in the study, and are able to provide informed consent will be eligible for the study.

The sterilization procedure will proceed as it would if the subject were not in the trial. For subjects who elect to have hysteroscopic sterilization, 3 months following the placement procedure, the subject will be scheduled to return to the physician’s office or radiology facility for a confirmation test to evaluate Essure insert location and retention. Upon a satisfactory confirmation test, subject will be instructed to rely on Essure for contraception.

Follow-up contact will take place at 3 months ( $\pm 2$  weeks), 12 months ( $\pm 4$  weeks), 24 months ( $\pm 4$  weeks), 36 months ( $\pm 4$  weeks), 48 months ( $\pm 4$  weeks), and 60 months ( $-4$  weeks,  $+1$  week) post procedure. These visits will collect information that includes (but is not limited to) pelvic / lower abdominal pain, bleeding, gynecological procedures, AEs, and concomitant medication use.

Patient reported outcomes for pain (Patient Reported Outcomes Measurement Information System Scale V1.0, Pain Intensity 3a and Pain Interference 8a Participant Format) will be assessed at Baseline, Week 1, Week 2, Week 3, Week 4, Month 2, Month 3, and then every 3 months starting Month 6 until 36, if the response is “Yes” to the question “Did you experience pain in your pelvic area or in your lower abdomen during the past week?”

Patient reported outcomes for bleeding (Aberdeen Menorrhagia Severity Scale) will be assessed at baseline and then every 3 months starting Month 3 until Month 36.

Patient reported outcomes for health status (Medical Outcomes Study Short Form-36) will be assessed at Baseline, Month 6, Month 12, Month 24, Month 36, and Month 60.

Subjects will also complete a baseline questionnaire (Fibromyalgia Survey Questionnaire) that may help to identify women who are more likely to report pain events.

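### The SAP's step-1 propensity-score list omits the pre-existing pain disorders that the protocol names, and an undefined rule lets that list become the final model, so the primary matched set may keep a modest imbalance in prior pain.

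*SAP*

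**What the plan says.** Protocol 10.3 lists variables likely to be in the PS model, among them "pre-existing pain disorders (pelvic pain, low back pain, chronic headache, fibromyalgia". It does not list pre-existing abnormal uterine bleeding (AUB).

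SAP 6.6.1, Table 5, has twelve rows. None is a pain variable; one is "Pre-existing abnormal uterine bleeding". The only support given is a footnote citing internal data.

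SAP 6.6.1 then builds the model in two steps.

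- Step 1: "In a first step, all above listed potential confounders are to be included in the stepwise model build procedure".
- Step 2: "In a second step, all other baseline data plus the list of potential confounders used for model build in the first step" go into a stepwise logistic regression.
- Choice between them: "If the contribution of the additional data is low, the PS built on the first model will be considered for analysis". The independent party proposes the final model, which is discussed with the FDA.

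SAP 5.1 makes the Adjusted Full Analysis Set primary if PS overlap is adequate. The preferred matching is 1:1 nearest neighbour with a caliper of 0.2 SD of the logit PS.

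The fibromyalgia questionnaire (FSQ), PROMIS, the Aberdeen bleeding scale (AMSS) and SF-36 are completed at the procedure visit (Protocol 9.2.2). None is in SAP Table 1 (baseline variables) or Table 5. SAP 3 describes the FSQ as a questionnaire "that may help to identify women who are more likely to report pain events".

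**The concern.** New or worsening chronic pelvic or lower abdominal pain is the first study objective. Women with existing pelvic pain may enrol at the investigator's discretion (Protocol 6.2, criterion 10). SAP Table 3 counts pelvic pain, lower back pain and dysmenorrhoea as outcome terms, which overlaps the protocol's list of pain disorders. Protocol 5.2.1 presents the FSQ as useful for predicting chronic pain. Prior pain is thus a likely predictor of the endpoint, and it may also influence the choice of method. The documents do not call it a confounder; that is an inference from these passages.

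Stepwise selection on treatment keeps variables that separate the groups clearly. It gives no protection to one that predicts the outcome strongly and differs only moderately between groups. At stake is avoidable bias in the primary pain comparison from information the study already holds.

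**Working it through.** **1. The two lists.** The protocol list and Table 5 each have twelve entries. Eleven match in topic: age, race, BMI, region, insurance, hormonal contraception, disorders associated with hysterectomy, gastrointestinal disorders, autoimmune disease, diabetes and hypertension. The twelfth is pain disorders in the protocol and AUB in the SAP. No reason is given for the exchange.

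**2. How pain can reach the final model.** It is not in step 1. At step 2 it is a candidate, since SAP Table 1 includes pelvic pain unrelated to menses and medical history. It must then survive stepwise selection, and the step-2 model must not be set aside. No entry level, metric or threshold is stated for either.

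**3. The pre-procedure questionnaire scores.** SAP 4.6.1 takes the last value at or before the index event as baseline, which includes them. SAP 6.6.1 treats anything measured after the treatment decision as an outcome; read literally, this excludes scores taken at the procedure visit. The two rules need reconciling.

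**4. Size.** The documents give no sample size, event risk or prevalence of prior pain, so there is no planned figure to reproduce. All inputs here are assumptions: chronic-pain risk 30% with and 8% without prior pain, prior pain in 10% of laparoscopic women, no device effect.

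Risk in a group = p × 0.30 + (1 − p) × 0.08.

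- Laparoscopic, p = 10%: 0.030 + 0.072 = 0.102.
- Essure, p = 15%: 0.045 + 0.068 = 0.113. Difference +1.1 points; risk ratio 0.113/0.102 = 1.11.
- Essure, p = 20%: 0.124; +2.2 points; 1.22.
- Essure, p = 25%: 0.135; +3.3 points; 1.32.

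With 10% in Essure and 15% in laparoscopic women the ratio is 0.102/0.113 = 0.90.

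A second set of assumptions uses the confounding ratio [1 + p1(R − 1)]/[1 + p0(R − 1)], with R the outcome risk ratio for prior pain. For p1 = 20% (Essure), p0 = 15% and R = 2 to 4 it gives 1.04 to 1.10. For p1 = 20%, p0 = 30% it gives 0.92 to 0.84.

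**5. Which imbalances would step 2 miss?** Assume entry at two-sided p < 0.05, a single-variable test, and 200 to 500 Essure women with twice as many laparoscopic women. Chance of entry = Φ[(|p1 − p0| − 1.96 × SE0)/SE1], where SE0 uses the pooled proportion and SE1 the separate ones. For 15% versus 10% with 200 and 400 women: SE0 = 0.0278, SE1 = 0.0294, (0.05 − 0.0545)/0.0294 = −0.15, so 44%.

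| Prior pain, Essure vs laparoscopic | Chance of entry, 200 to 500 Essure | Standardised difference |
|---|---|---|
| 15% vs 10% | 44% to 80% | 0.15 |
| 20% vs 15% | 35% to 68% | 0.13 |
| 25% vs 20% | 29% to 60% | 0.12 |
| 20% vs 10% | 91% to 99.9% | 0.28 |
| 25% vs 10% | over 99% | 0.40 |

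Five-point differences can escape; 10- and 15-point differences seldom would. The realistic exposure is therefore the +1.1-point case.

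**6. Cost of forcing pain in.** A simulation (200 runs of 900 women; odds ratio 1.7 for choosing Essure given prior pain; outcome risk 24% with and 8% without; no device effect; 1:1 matching at the planned caliper) compared the PS without and with pain.

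- Without pain: matched prior pain 26.3% vs 17.2%, standardised difference 0.22, spurious risk ratio 1.13.
- With pain forced in: 24.3% vs 24.4%, 0.00, risk ratio 1.00.
- Essure women matched: 97% and 96%.

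This imbalance is larger than the one likely to escape step 2, so the run shows the mechanism and the cost, not the expected bias.

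**The case against.** The plan has real safeguards. SAP 4.5.1 gives the independent party all baseline data and SAP 6.6.1 makes every baseline variable a candidate. Table 1 holds pelvic-pain history, dysmenorrhoea, dyspareunia and prescribed medication for lower abdominal pain. Endometriosis, fibroids and gastrointestinal disorders are already in step 1. Balance is examined variable by variable (6.6.1), and Table 1 is tabulated for the adjusted set (6.1.1, 6.6.2). Protocol 10.5 reassesses balance at three years and at study end. The step-1 model is only a candidate for use, subject to FDA discussion. SAP 6.4.4 allows Cox adjustment for pre-existing conditions, and SAP 6.7 analyses subgroups by baseline FSQ. A low contribution to a treatment model also implies little imbalance. The analysis is declared exploratory.

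Most of this stands, and it limits the size of the problem. What remains is that being considered is not being included. The balance checks have no acceptance limit, the Cox covariates are optional and do not name pain, and subgrouping is not adjustment. Controlling measured confounding is the stated aim of SAP 6.6, whether or not tests are confirmatory.

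**Conclusion.** The discrepancy is real. Following the SAP as written can leave a modest imbalance in prior pain in the primary matched set. Under the stated assumptions the plausible effect is about one percentage point (risk ratio about 1.1), in either direction.

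A reader might infer more than the documents support:

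- That matching is the only control of confounding. SAP 6.4.4 allows covariates; matching is the only control firmly specified.
- That the SAP ignores baseline pain altogether. It is missing from Table 5, but remains a step-2 candidate. The protocol's own list does not name the questionnaire scores either.
- That the bleeding comparison is generally biased. Pre-existing AUB is in Table 5; only the AMSS score is unlisted.
- That the bias could be 2 to 3 points. Imbalances that large would usually be picked up at step 2.
- That physician-experience variables must be excluded. Nothing shows they are unrelated to outcome, and SAP 6.6.1 already calls for care with strong predictors of treatment choice.
- That the independent party works from outcome data because it "has only access to the treatment variable and the baseline variables listed in" Table 2. The sentence itself says baseline variables, so this is a clerical slip for Table 1.

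**What to change.** 1. Add pelvic pain, low back pain, chronic headache and fibromyalgia to Table 5, and keep pre-existing AUB.
2. Force these into the PS model with the baseline FSQ, pain screening question and AMSS score, whatever the stepwise result or the step-2 contribution. PROMIS is completed only after a positive screening answer. Make a negative answer its own category and use PROMIS scores only among women who answered yes.
3. State that questionnaires completed before the procedure count as baseline under SAP 4.6.1, despite the post-decision rule in 6.6.1.
4. Report standardised mean differences for the forced variables in the matched set, with a target below 0.10. Adjust the outcome model for any that miss it.
5. Apply this at the PS re-evaluation allowed by Protocol 10.5, outcome-blinded, using baseline data from all women in the Full Analysis Set.
6. Correct the table reference from Table 2 to Table 1.

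The cost is SAP wording and one rerun on data already collected. The downside is slightly fewer matched pairs. In the simulation one added variable lowered the matched share by one percentage point; forcing several could lower it more.

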#### **6.6.2 Analysis based on different analysis set**

All the baseline characteristics defined in [Table 1](#), main endpoints variables defined in [Table 2](#), and summary AEs will be analyzed using full analysis set, adjusted full analysis set, reliance set and adjusted reliance set with adjusted full analysis set being the primary analysis.

Descriptive analyses of the PRO questionnaires will be done using full analysis set, adjusted full analysis set, reliance set and adjusted reliance set with adjusted full analysis set being the primary analysis.

For other outcome variables listed in [Table 2](#) and AEs by PT and SOC, the analysis will be conducted using the full analysis set and adjusted full analysis set.

For device events, the analysis will be conducted based the full analysis set using all the data till the end of study.

## 6.7 Subgroup analysis

Subgroup analysis will be conducted for main endpoints, summary AEs, and device events for the following groups:

- Types of laparoscopic procedures (Total Salpingectomy, Partial Salpingectomy, Tubal Cauterization, Fallope Ring, Filshie Clip, Hulka Clip and other)
- Age ( $\leq 30$  years,  $> 30$  years)
- Number of births (0, 1-3, 4+)
- FSQ at baseline (FSQ $<13$ , FSQ $\geq 13$ )

## 6.8 Sensitivity analyses

Sensitivity analysis will be performed for the main endpoints and summary AEs. The analysis will include all the data from index date till the end of study no matter if the subject had censoring events or not during the study.

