- Levels of inflammatory markers and HLA type in subjects with Essure and adjudicated hypersensitivity reactions can be compared to corresponding findings in subjects with Essure without hypersensitivity reactions as well as to laboratory results in laparoscopic tubal ligation subjects (with and without adjudicated hypersensitivity reactions). Serum cytokine values will be classified as below the normal range, within the normal range, or above the normal range, as appropriate. These values will be used to provide descriptive summaries of change of categories between baseline and

Year 1 and between baseline and Year 5. For these analyses the safety population will be used to present data by treatment groups and by symptomatic/asymptomatic subjects. Secondary analyses can also be performed in subjects who report positively to events on the Supplementary PRO tools (e.g. fatigue, headache) versus those who do not. These comparisons will not rely on device removal.

- Serum or plasma nickel and titanium levels in subjects with Essure and adjudicated hypersensitivity reactions can be compared to serum or plasma nickel and titanium levels in subjects with Essure without hypersensitivity reactions as well as to serum or plasma nickel and titanium levels in laparoscopic tubal ligation subjects (with and without adjudicated hypersensitivity reactions). Secondary analyses can also be performed in subjects who report positively to events on the Supplementary PRO tools (e.g. fatigue, headache) versus those who do not. These comparisons will not rely on device removal.
- NiLPT and chromium LPT results (both the continuous measurement as well as the positive / negative assessment) in subjects with Essure and adjudicated hypersensitivity reactions can be compared to NiLPT and chromium LPT results in subjects with Essure without hypersensitivity reactions as well as to NiLPT and chromium LPT results in laparoscopic tubal ligation subjects (with and without adjudicated hypersensitivity reactions). Secondary analyses can also be performed in subjects who report positively to events on the Supplementary PRO tools (e.g. fatigue, headache) versus those who do not. These comparisons will not rely on device removal.
- An individual subject's serum or plasma nickel and titanium levels and NiLPT can be compared to baseline levels in order to assess any change. In addition, in cases of removal, subsequent post-removal levels can also be compared.

Autoimmune diseases

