9.6.1.6 Device removal and surgical pathology

Section modified by Amendment 1 (Section 16.1) and Amendment 2 ([Modification 5](#)).

Each time a surgical procedure is performed (Essure or laparoscopic tubal ligation), additional information will be collected about the circumstances surrounding the surgery (e.g., date of placement, reason for removal, procedure details, any energy sources used, vasoconstrictive agent used, imaging to assist with confirming the location of the insert, and the location and status of the device removed). Subjects who have had surgical intervention or their device removed will continue to be followed for the collection of safety and laboratory data.

Prior to any planned surgical removal of an Essure insert, salpingectomy, or hysterectomy, the investigator must contact the sponsor in order to arrange for handling of the pathology specimen. This is important as improper handling of specimens may preclude the performance of metallurgic analyses.

Whenever possible, and if clinically and surgically appropriate, if the decision is to remove the fallopian tube, this should be done with the Essure insert or sterilization device, if

applicable (e.g., Falope ring, Filshie clip) in situ. In the case of Essure, this can be accomplished by making a circumferential incision around the proximal tube near the cornua, then pulling the proximal most portion of the insert from the cornua (while the remainder of the insert remains in the tube that is removed), or with a cornual resection. Physician judgment as to the appropriate procedure for the subject will take precedence over obtaining a pathology specimen. If a hysterectomy is clinically and surgically appropriate, it should be performed with the tubes attached to the uterus, if possible.

In the Essure group, ideal specimens will have the Essure insert in situ as this will provide the most complete information; however, all tubes, regardless of presence of the insert, should be submitted for examination. In addition, all inserts, regardless of whether they are in situ or previously removed, should be submitted. Processing for tubes with and without inserts in situ will need to be slightly different.

In the laparoscopic sterilization group, ideal specimens will be fallopian tubes with sterilization devices in situ, if applicable (e.g., Falope ring, Filshie clip); however, all tubes should be submitted regardless of presence of a previously applied sterilization device.

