### **4.3 Handling of loss to follow-up, premature discontinuation, and censoring**

Subjects who leave the study before reaching the study completion assessment five years after start of the sterilization procedure will be included in the analysis populations, since the analyses are based on all subjects who attempt sterilization.

For subjects who attempt two sterilization methods, or have any hysterectomy (subtotal, total or radical), or have Essure complete removal using a salpingectomy, or device removal not accompanied by sterilization procedure, their data will be censored for analysis purpose on the earliest date of second sterilization method, hysterectomy surgery date, or Essure removal date, for the primary analysis.

Data will be collected for all the subjects until the end of study or early termination.

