#### **6.4.5 Procedure failures that are converted to alternative permanent sterilizations**

A conversion is defined as the change of treatment agent from Essure to laparoscopic tubal sterilization. It is also possible that a subject may convert from an unsuccessful laparoscopic tubal sterilization to Essure.

Subjects will be analyzed according to the group based on the initial index event. All the variables will be summarized from subjects' enrollment till end of study or censoring date. The subjects will be followed for safety monitoring until the end of study no matter if the subjects had attempted alternate permanent sterilization procedure or not.

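### By-visit PRO and laboratory summaries appear to stop at removal, hysterectomy or a second method, and no final analysis restores the later values

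*SAP*

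**What the plan says.** SAP 4.3 applies to women who attempt two methods, have any hysterectomy, or "have Essure complete removal using a salpingectomy, or device removal not accompanied by sterilization procedure". For these women "their data will be censored for analysis purpose on the earliest date of second sterilization method, hysterectomy surgery date, or Essure removal date", and the sentence ends by tying this to the primary analysis. SAP 6.4.5, on conversions between methods, says that every variable is summarized from "enrollment till end of study or censoring date".

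On PRO data, SAP 6.4.6 says only that longitudinal analysis is descriptive. SAP 6.6.2 adds the analysis sets: "Descriptive analyses of the PRO questionnaires will be done using full analysis set", then the adjusted full analysis set and the two reliance sets, with the adjusted full analysis set as primary. On laboratory data, SAP 6.4 promises change from baseline at each post-baseline visit.

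Collection does not stop at the cut. SAP 4.3 states: "Data will be collected for all the subjects until the end of study or early termination". Protocol 9.6.1.6 states: "Subjects who have had surgical intervention or their device removed will continue to be followed for the collection of safety and laboratory data". Protocol 9.6.1.1 says of nickel, titanium and NiLPT that "in cases of removal, subsequent post-removal levels can also be compared". Protocol 9.6.1.6 goes further and says that tissue metal results will be correlated with blood levels from before and after removal.

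SAP 6.8 provides the analysis that ignores censoring: "Sensitivity analysis will be performed for the main endpoints and summary AEs".

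**The concern.** A woman who has her device removed, or has a hysterectomy, may be doing so because of pain or bleeding. If her questionnaire and laboratory values are dropped from that date, later by-visit tables lose a group that may differ from those who remain, and the loss need not be equal between arms. Essure removal is a trigger that only a woman who received Essure can meet. A woman who converted from laparoscopic sterilization to Essure is already censored at her second method.

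PRO results are reported only descriptively. Which women stand behind each mean or percentage is therefore a large part of the result. The plan allows an uncensored look at main endpoints, summary AEs and device events, but not at PRO and laboratory values. The post-removal comparisons foreseen in the protocol rely on samples that, in a censored woman, all fall after her cut.

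**Working it through.** The documents give no figure on this point to reproduce, so the check is mainly of text.

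**1. Does the cut reach PRO and laboratory values?** SAP 4.3 censors the woman's data, not only her events, for the primary analysis. SAP 6.6.2 names a primary analysis for the PRO questionnaires. SAP 6.4.5 applies the censoring date to all variables. Sections 6.4 (laboratory), 6.4.6 (longitudinal) and 4.6.3 (visit labels) contain no exemption. The cut therefore applies on a plain reading, but by inference.

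**2. Which final outputs use data after the cut?**

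| Output | SAP section | By-visit PRO or laboratory values? |
|---|---|---|
| Sensitivity analysis, main endpoints and summary AEs | 6.8 | No |
| Device events, all data to end of study | 6.6.2 | No |
| AEs after censoring, by censoring reason | 6.5.1 Adverse events | No |

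Three outputs use such data. None covers PRO or laboratory values.

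**3. Do later values exist?** Protocol Table 9–2 and sections 9.2.2.10 and 9.2.2.11 schedule PROMIS and AMSS at months 48 and 60. The protocol synopsis, Protocol 9.2.2.2 and SAP 3 end them at month 36. Supplemental PROs and SF-36 run to month 60. Protocol 9.6.3.1 draws serum nickel at baseline, 12 and 60 months, titanium at baseline and 1 year, and routine NiLPT at baseline and 12 months, with unscheduled draws for symptoms. Later data exist, but they are thin for titanium and NiLPT.

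**4. What could the cut do to a by-visit result?** Let r be the share of an arm censored before a visit, and d the mean of censored minus uncensored women at that visit, using actual values after the event.

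All-data mean − censored mean = (1 − r)·M + r·(M + d) − M = r·d

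Neither r nor d is in the documents. Over an assumed range, in T-score points:

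| r | d = −5 | d = 0 | d = +5 | d = +10 |
|---|---|---|---|---|
| 5% | −0.25 | 0 | +0.25 | +0.5 |
| 10% | −0.5 | 0 | +0.5 | +1.0 |
| 20% | −1.0 | 0 | +1.0 | +2.0 |
| 30% | −1.5 | 0 | +1.5 | +3.0 |

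For the proportion with T-score 60 or more, assume 15% among uncensored women and q among censored women. The all-data proportion is (1 − r)·0.15 + r·q:
- q = 15%: 15.0% at any r
- r = 10%, q = 45%: 0.135 + 0.045 = 18.0%
- r = 30%, q = 45%: 0.105 + 0.135 = 24.0%
- q below 15%: under 15.0%

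The effect on the comparison between arms is r·d in the Essure arm minus r·d in the laparoscopic arm. With r of 10% and 5% and d = +5 in both, it is 0.5 − 0.25 = +0.25 points. With d = −5 it is −0.25. The sign follows d, which is unknown because symptoms may resolve or persist after surgery.

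This is illustration, not an estimate. PROMIS is completed only after a positive pain screen, so a score mean has a further selection step that the formula leaves out.

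**The case against.** **The cut is not stated outright for these data.** SAP 6.1.3 defines the risk period for safety outcomes, and the wording in 6.4.5 stands in a section on conversions. That is fair, and it makes clarification the first step. Nothing says that these data are exempt, however, and a programmer following 4.3 and 6.4.5 would cut them.

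**The main endpoints are protected.** Pain and bleeding rest on AE reports, with PRO alerts prompting assessment, and 6.8 gives them an uncensored analysis. Surgery, including device removal, is itself a main endpoint. The study is exploratory. All this stands, and it confines the point to PRO and laboratory summaries.

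**The loss may already be partly visible.** SAP 4.2 and 4.4.6 include missing values in the denominator of percentages. If censored women stay there, the example with r = 10% and 15% among uncensored women prints 0.90 × 15% = 13.5% and at least 10% missing. That row would not separate removal or hysterectomy from ordinary non-response, and it does not help with means.

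**Interim reports may help.** SAP 7 uses all data to the cutoff without saying whether censoring applies. Protocol 10.5 includes serology at the 3-year interim, and device removals with outcomes and resolutions when linked to an AE. Neither supplies the final analysis.

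**Stronger readings are not supported.** A reader might infer that by-visit results describe only women who kept the method. They do not. Women contribute every visit before their event, women with failed placement and no second method remain in the full analysis set, and removals outside the types listed in 4.3 are not clearly censored. A reader might also infer that each exit makes an arm look better. A second method after failed placement need not involve pain, and Protocol 9.6.1.6 foresees tubes removed for unrelated reasons.

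**Conclusion.** The concern holds in limited form. As written, the SAP removes by-visit PRO and laboratory values after a second method, hysterectomy or Essure removal, and no final output brings them back. Each summary describes women not yet censored at that visit. The loss may be informative, and one of its triggers is specific to Essure.

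The size and direction of any distortion cannot be derived from the documents. Under the assumed inputs above, the shift in one arm's mean runs from −1.5 to +3.0 T-score points, with zero inside the range. A reader might try to carry censored women forward at their scores from before surgery and call the result a hidden difference between arms. The documents do not support that, because an all-data analysis would use the values actually observed afterwards.

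The conclusion rests on reading 4.3 and 6.4.5 as covering these variables. If the sponsor intends no cut, the SAP should say so. The change should be made, since it determines which women the PRO and laboratory results describe.

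**What to change.** 1. State in SAP 6.4 and 6.4.6 whether by-visit PRO and laboratory summaries are censored, and at which events. The list in 6.1.3 includes the start of hormonal manipulation, and the list in 4.3 does not.
2. In SAP 6.8, extend the all-data analysis to these summaries: index date to end of study, by initial arm, regardless of censoring events.
3. In the censored version, print the number censored by reason for each arm and visit. Show AMSS after hysterectomy as its own category.
4. Where samples exist, add a descriptive table of post-removal nickel, titanium and NiLPT values, as foreseen in Protocol 9.6.1.1 and 9.6.1.6. Note that NiLPT after month 12 comes only from unscheduled draws.

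The cost is SAP wording, reruns of existing table programs and some added tables, with no new data collection. The drawback is that all-data values mix time with and without the method, so they belong beside the censored version and should not replace it.
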